4.2. Scientific rationale for study design

Vaccination programs with SARS-CoV-2 mRNA vaccines have been implemented in many countries worldwide. SARS-CoV-2 mRNA vaccines are administered throughout the year and may thus be administered around the same time when the RSVPreF3 OA investigational vaccine may potentially be recommended for immunization against RSV infection. To date, there is no data available on the safety and immunogenicity of the RSVPreF3 OA investigational vaccine when it is co-administered with a SARS-CoV-2 mRNA vaccine.

RSV is associated with serious illness in OA and high-risk adults, including those with chronic lung and heart disease or other co-morbidities that may lead to increased risk of RSV-LRTD. A large US prospective, population-based study reported the overall annual estimated incidence of RSV infection during 3 seasons among different age groups, in two different settings (New York City and Rochester). The specific estimated incidence ranged from 7.7–11.9/100 000 population, 33.5–57.5/100 000, and 136.9–255.6/100 000 in patients 18–49, 50–64, and ≥65 YOA, respectively. Moreover, the incidence of RSV infection in hospitalized adults of 50–64 and ≥65 YOA was approximately 5 and 15 times higher, respectively, than incidence among patients 18–49 YOA [Branche, 2022]. In another prospective study it was determined that the hospitalization rates for RSV were similar to those associated with influenza in adults aged ≥50 YOA [Widmer, 2012].

The US FDA and the EMA have authorized the Comirnaty Omicron XBB.1.5 30 micrograms/dose dispersion as a single dose for injection for active immunisation to prevent COVID-19 caused by the SARS-CoV-2, in individuals 12 years of age and older [Comirnaty product information package insert, EMA, 2023; US FDA, 2023].

Both RSVPreF3 OA investigational vaccine and SARS-CoV-2 vaccines will be available for individuals within similar age groups. These data are expected to help public health authorities provide more evidence-based guidance and health care providers to make decisions on such vaccine co-administrations.

The current study is therefore designed to assess the safety, reactogenicity and immunogenicity of the RSVPreF3 OA investigational vaccine when it is co-administered with a COVID-19 mRNA vaccine, compared to administration of the vaccines separately in adults aged 50 years and above.

As the RSVPreF3 OA investigational vaccine is adjuvanted, all participants will be followed up for safety for 6 months post-RSV investigational vaccine administration.

4.2.1. Participant input into design

Not applicable.

4.3. Justification for dose

A single dose (0.5 mL) of the licensed formulation (120 µg RSVPreF3/AS01E) will be used in this study.

In the current study, the authorized Comirnaty Omicron XBB.1.5 30 micrograms/dose dispersion for injection will be administered.

4.4. End-of-study definition

A participant is considered to have completed the study if the participant has completed all periods of the study including the last scheduled contact as described in the protocol.

EoS: LSLV (contact at 6 months post-last dose) or Date of the last testing/reading released of the Human Biological Samples, related to primary and secondary endpoints, whichever occurs later. EoS must be achieved no later than 8 months after LSLV. EoS cannot be before LSLV.

5. STUDY POPULATION

Prospective approval of protocol deviations to recruitment and enrollment criteria, also known as protocol waivers or exemptions, is not permitted.

5.1. Inclusion criteria

Participants are eligible to be included in the study only if all of the following criteria apply:

- Participants, who, in the opinion of the investigator, can and will comply with the requirements of the protocol (e.g., completion of the diary cards, return for follow-up visits). **INC#1**
 - Note: In case of physical incapacity that would preclude the self-completion of the diary cards, either site staff can assist the participant (for activities performed during site visits) or the participant may assign a caregiver to assist him/her with this activity (for activities performed at home). However, at no time will the site staff or caregiver evaluate the participant's health status while answering diaries or make decisions on behalf of the participant.
- Written or witnessed informed consent obtained from the participant (participant must be able to understand the informed consent) prior to performance of any studyspecific procedure. INC#2
- A male/female of ≥50 YOA at the time of the first study intervention administration. **INC#3**
- Participants who are medically stable in the opinion of the investigator at the time of first vaccination. Participants with chronic stable medical conditions with or without

217848 (RSV OA=ADJ-013) Protocol Final

specific treatment, such as diabetes, hypertension or cardiac disease, are allowed to participate in this study if considered by the investigator as medically stable. INC#4

A stable medical condition is defined as disease not requiring significant change in therapy or hospitalization for worsening disease during the 3 months before enrollment.

- Participants living in the general community or in an assisted-living facility that
 provides minimal assistance, such that the participant is primarily responsible for
 self-care and activities of daily living. INC#5
- Participants who have received previously a SARS-CoV-2 vaccine, being administered at least 3 months prior to study vaccination. **INC#6**
- Female participants of non-childbearing potential may be enrolled in the study. Non-childbearing potential is defined as hysterectomy, bilateral oophorectomy, bilateral salpingectomy, and post-menopause. **INC#7**
- Female participants of childbearing potential may be enrolled in the study if the participant. **INC#8**
 - has practiced adequate contraception from 1 month prior to study intervention administration and agreed to continue adequate contraception for at least 1 month after the last vaccination.
 - has a negative pregnancy test on the day of and prior to study intervention administration.

Refer to Section 10.4.1 for definitions of women of childbearing potential, non-childbearing potential, menarche and menopause and section 10.4.2 on adequate contraception.

5.2. Exclusion criteria

Participants are excluded from the study if any of the following criteria apply:

5.2.1. Medical Conditions

- History of any reaction or hypersensitivity likely to be exacerbated by any component of the study interventions, including a known history of severe allergic reaction (e.g., anaphylaxis) (For details on components of study interventions administered, refer to Table 5, [Arexvy Prescribing Information package insert, 2023] [Arexvy Summary of Product Characteristics, 2023] and Comirnaty Omicron XBB.1.5 COVID-19 mRNA vaccine SmPC/Prescribing information). EXC#1
- Any confirmed or suspected immunosuppressive or immunodeficient condition, resulting from disease (e.g., current malignancy, human immunodeficiency virus) or immunosuppressive/cytotoxic therapy (e.g., medication used during cancer chemotherapy, organ transplantation, or to treat autoimmune disorders), based on medical history and physical examination (no laboratory testing required). EXC#2
- Any history of myocarditis or pericarditis. **EXC#3**

217848 (RSV OA=ADJ-013) Protocol Final

- Recurrent history or uncontrolled neurological disorders or seizures. Participants with medically-controlled active or chronic neurological diseases can be enrolled in the study as per investigator assessment, provided that their condition will allow them to comply with the requirements of the protocol (e.g. completion of diary cards, attend regular phone calls/study site visits). **EXC#4**
- Serious or unstable chronic illness. EXC#5
- Any history of dementia or any medical condition that moderately or severely impairs cognition. EXC#6
 - Note: If deemed necessary for clinical evaluation, the investigator can use tools such as Mini-Mental State Examination (MMSE), Mini-Cog or Montreal Cognitive Assessment (MoCA) to determine cognition levels of the participant.
- Significant underlying illness that in the opinion of the investigator would be expected to prevent completion of the study (e.g., life-threatening disease likely to limit survival up to study end). **EXC#7**
- Any medical condition that in the judgment of the investigator would make intramuscular injection unsafe. **EXC#8**
- Any SAE attributed to a previous dose of the SARS-CoV-2 mRNA vaccine. **EXC#9**
- Any other clinical condition that, in the opinion of the investigator, might pose additional risk to the participant due to participation in the study. **EXC#10**
- Recent SARS-CoV-2 infection within 3 months prior to the COVID-19 vaccine dose administration. Timelines to be determined from symptoms onset or positive COVID-19 test (if infection was asymptomatic). EXC#11

5.2.2. Prior/Concomitant Therapy

- Use of any investigational or non-registered product (drug, vaccine or invasive medical device) other than the study interventions during the period beginning 30 days before the first dose of study interventions and ending 30 days after the last vaccine administration, or their planned use during the study period. EXC#12
 - Note: EEC directive 93/42/EEC defines an invasive medical device as 'A device which, in whole or in part, penetrates inside the body, either through a body orifice or through the surface of the body'.
- Planned administration of a vaccine in the period starting 30 days before the first dose and ending 30 days after the last dose of study intervention(s) administration*, with the exception of inactivated and subunit influenza vaccines which can be administered up to 14 days before or from 14 days after the study vaccination.
 EXC#13
 - *If emergency mass vaccination for an unforeseen public health threat (e.g., a pandemic) is recommended and/or organized by public health authorities outside the routine immunization program, the time period described above can be reduced if necessary for that vaccine, provided it is used according to the local governmental recommendations and Sponsor is notified.

- Chronic administration of immune-modifying drugs (defined as more than 14 consecutive days in total) and/or planned use of long-acting immune-modifying treatments at any time up to the last blood sampling visit. **EXC#14**
 - Up to 3 months prior to the study intervention administration:
 - o For corticosteroids, this will mean prednisone equivalent ≥ 20 mg/day. Inhaled and topical steroids are allowed.
 - Administration of immunoglobulins and/or any blood products or plasma derivatives.
 - Up to 6 months prior to study intervention administration: long-acting immune-modifying drugs including among others immunotherapy (e.g., TNFinhibitors), monoclonal antibodies and antitumoral medication.
- Administration of any SARS-CoV-2 vaccine during the 3 months preceding the study COVID-19 mRNA vaccine administration. EXC#15
- Previous vaccination with licensed or investigational RSV vaccine. **EXC#16**

5.2.3. Prior/Concurrent Clinical Study Experience

• Concurrently participating in another clinical study, at any time during the study period, in which the participant has been or will be exposed to an investigational or a non-investigational intervention (drug/invasive medical device). EXC#17

5.2.4. Other Exclusion Criteria

- Pregnant or lactating female participant. EXC#18
- Female participant planning to become pregnant or planning to discontinue contraceptive precautions. **EXC#19**
- History of chronic alcohol consumption and/or drug abuse as deemed by the investigator to render the potential participant unable/unlikely to provide accurate safety reports or comply with study procedures. **EXC#20**
- Participation of any study personnel or their immediate dependents, family, or household members. **EXC#21**
- Planned move during the study conduct that prohibits participation until study end.
 EXC#22

41

• Bedridden participants. EXC#23

5.3. Lifestyle considerations

Not applicable for this study.

5.4. Screen failures

A screen failure occurs when a participant who consents to participate in this study but is not entered in the study/randomized to a study intervention.

For screen-failed participants, limited data for screen failures (including demography, medical and vaccination history, eligibility criteria, concomitant medication, reason for screen failure and any SAEs that occurred at the visit) will be collected and reported in the eCRF to meet the CONSORT publishing requirements and to respond to queries from regulatory authorities.

5.5. Criteria for temporarily delaying enrollment/ administration of study intervention

Study intervention administration may be postponed within the permitted time interval as deemed appropriate by the investigator until transient conditions cited below are resolved. Participants meeting these criteria at Visit 1 will be considered screen failures if enrollment has closed once the condition(s) has/have resolved:

- Acute disease and/or fever at the time of study intervention administration. Refer to the SoA (Section 1.3) for definition of fever and preferred location for measuring temperature in this study.
- Participants with a minor illness (such as mild diarrhea, mild upper respiratory infection) without fever may be enrolled and/or dosed at the discretion of the investigator.
- Participants with symptoms suggestive of active COVID-19 infection (e.g., fever, cough, etc.). The return of the participant to the site will follow the specific guidance from local public health and other competent authorities (e.g. free of symptoms, COVID-19 negative testing, etc.). Please refer to Exclusion criteria Section 5.2.1 for time interval for study COVID-19 vaccination after a recent COVID-19 infection.
- In case of administration of inactivated, subunit or split influenza vaccines (fully licensed): postponement of study intervention administration within given protocol timelines and prior to the end of the study enrollment period, to allow respect of at least 14 days interval between above mentioned influenza vaccination and study intervention administration.
- Other issues (e.g., technical or administrative) preventing dose administration on day of visit.

All efforts should be made so that blood sample is taken on the same date as vaccination. For Visit 1, if the planned study intervention administration is delayed, blood sampling does not need to be repeated if it was obtained during enrollment visit. The following procedures must be repeated prior to the delayed study intervention administration:

- Urine pregnancy test
- Body temperature
- Re-check contraindications, warnings, and precautions to study intervention

• Re-check inclusion/exclusion criteria

Visit window for Visit 2 starts from day of first study intervention administration.

For delay in the study intervention administration during Visit 2 (control group) the following procedures must be repeated:

- Urine pregnancy test
- Body temperature
- Re-check contraindications, warnings, precautions to study intervention
- Re-check inclusion/exclusion criteria

6. STUDY INTERVENTIONS AND CONCOMITANT THERAPY

The definition of study intervention is provided in the table of Definition of terms.

6.1. Study interventions administered

Refer Section 4 for the study intervention administration schedule.

Table 5 Study Intervention(s) Administered

Study intervention name:	RSVPreF3 OA inv	estigational vaccine	Comirnaty Omicron XBB.1.5 COVID-19 mRNA vaccine
Study intervention formulation:	RSVPreF3 (120 µg)	AS01 _E : QS-21* (25 μg), MPL (25 μg), liposomes; Water for injections	Raxtozinameran (30 µg) embedded in LNP; Water for injections
Presentation:	Powder for suspension for injection; in vial	Suspension for suspension for injection; in vial	Dispersion for injection; in vial
Туре:	Inv	restigational	Comparator
Product category:		Biological	Biological
Route of	l II	M injection	IM injection
administration:			
Administration site:			
 Location 	Deltoid		Deltoid
 Directionality 	Upper		Upper
 Laterality ** 	Co-ad group: Dominant		Co-ad group: Non-dominant
•	Control gr	oup: Non-dominant	Control group: Non-dominant
Number of doses to be administered:		1	1
Volume to be	0.5 mL		0.3 mL
administered by dose ***			
Packaging and	Refer to the ph	armacy manual for more	Refer to the pharmacy
labelling:		details	manual for more details
Manufacturer:	GSK	Biologicals SA	Pfizer-BioNTech

IM: Intramuscular; LNP: Lipid nanoparticle; MPL: Monophosphoryl lipid A.

217848 (RSV OA=ADJ-013) Protocol Final

Study participants must be observed closely for at least 30 minutes after the administration of the study interventions. Appropriate medical treatment must be readily available during the observation period in case of anaphylaxis, syncope.

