3.2.2. Safety Objectives

The secondary question of interest is to evaluate the safety and reactogenicity following administration of the RSVPreF3 OA investigational vaccine and a dose of COVID-19 mRNA vaccine, co-administered or administered alone.

		Attributes				
Treatment Population		Endpoint (Variable)		Intercurrent ev	Summary measure	
Heatment	i opulation	Enapoint (variable)		Description	Handling strategy	
Co-ad group: COVID- 19 mRNA vaccine at Day 1 and RSVPreF3 OA investigational vaccine at Day 1 Control group: COVID-19 mRNA vaccine at Day 1 and RSVPreF3 OA investigational vaccine at Day 31	Adults ≥50 years at the time of first vaccination	 Occurrence of each solicited administration site event with onset within 4 days after study intervention administration. Occurrence of each solicited systemic event with onset within 4 days after study intervention administration. Occurrence of unsolicited AEs within 30 days after study intervention administration. Occurrence of SAEs after study intervention administration (Day 1) up to study end (6 months after last study intervention administration). Occurrence of pIMDs after study intervention administration (Day 1) up to study end (6 months after last study intervention administration). 	2.	Study vaccination not administered as per protocol. Prohibited medication, vaccination or intercurrent medical condition prior to the blood sample.	All the data collected for the variable of interest are used regardless of whether the intercurrent event occurs (treatment policy).	The percentage of participants by group who report each of the endpoint.

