6.3. Assignment to study intervention

6.3.1. Participant identification

Participant identification numbers will be assigned sequentially to the individuals who have consented to participate in the study. Each study center will be allocated a range of participant identification numbers.

^{*} QS-21: Quillaja saponaria Molina, fraction 21 (Licensed by GSK from Antigenics Inc, a wholly owned subsidiary of Agenus Inc., a Delaware, USA corporation).

^{**} The non-dominant arm is the preferred arm of injection. In case it is not possible to administer the study intervention in the non-dominant arm, an injection in the dominant arm may be performed.

^{***} Refer to the pharmacy manual for the volume after re-constitution.

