10.3.5.2. Assessment of intensity

The investigator will make an assessment of intensity for each AE, AESIs, SAE and pegnancies reported during the study and assign it to one of the following categories:

• Mild:

A type of AE that is usually transient and may require only minimal treatment or therapeutic intervention. The event does not generally interfere with usual activities of daily living.

Moderate:

A type of AE that is usually alleviated with additional specific therapeutic intervention. The event interferes with usual activities of daily living, causing discomfort but poses no significant or permanent risk of harm to the research participant.

• Severe:

A type of AE that interrupts usual activities of daily living, or significantly affects clinical status, or may require intensive therapeutic intervention.

The intensity of the following solicited AEs will be assessed as described:

Table 18 Intensity scales for solicited events in participants ≥50 YOA

Event	Intensity grade	Parameter
Pain at administration site	0	None
	1	Mild: Any pain neither interfering with nor preventing
		normal everyday activities.
	2	Moderate: Painful when limb is moved and interferes with
		everyday activities.
	3	Severe: Significant pain at rest. Prevents normal
		everyday activities.
Redness at administration site	See Table 16	Greatest surface diameter in mm
Swelling at administration site	See Table 16	Greatest surface diameter in mm
Temperature*	See Table 17	Temperature in °C/°F
Headache	0	None/Normal**
	1	Mild: Headache that is easily tolerated
	2	Moderate: Headache that interferes with normal activity
	3	Severe: Headache that prevents normal activity
Fatigue	0	None/Normal**
	1	Mild: Fatigue that is easily tolerated
	2	Moderate: Fatigue that interferes with normal activity
	3	Severe: Fatigue that prevents normal activity
Myalgia	0	None/Normal**
	1	Mild: Myalgia present but does not interfere with activity
	2	Moderate: Myalgia that interferes with normal activity
	3	Severe: Myalgia that prevents normal activity
Arthralgia	0	None/Normal**
	1	Mild: Arthralgia present but does not interfere with activity
	2	Moderate: Arthralgia that interferes with normal activity
	3	Severe: Arthralgia that prevents normal activity

^{*} Refer to SoA (Section 1.3) for the definition of fever and the preferred location for temperature measurement.

The maximum intensity of local injection site erythema/swelling and fever will be scored at GSK as follows:

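### Table 5 puts the RSV vaccine in the dominant arm in Co-Ad and the non-dominant arm in Control, so RSV-site local reactions are largely aliased with arm; the SAP should add a comparison at the COVID-19 site

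*Protocol*

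**What the plan says.** Protocol 6.1, Table 5, fixes the side of injection by vaccine and group. The RSV vaccine is "Co-ad group: Dominant", and its Control entry is non-dominant. The COVID-19 vaccine is "Co-ad group: Non-dominant", and non-dominant in Control as well. The schedule of activities (Protocol 1.3, Table 1) requires the two Co-Ad injections to be in separate arms.

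The double-asterisk footnote to Table 5 says "The non-dominant arm is the preferred arm of injection". If that arm cannot be used, "an injection in the dominant arm may be performed".

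Protocol 3.2.2 makes local reactogenicity of the two vaccines, together or alone, a secondary objective. Table 18 (Protocol 10.3.5.2) grades site pain by use of the limb: Grade 2 begins "Moderate: Painful when limb is moved and interferes with" everyday activities. Redness and swelling are graded in millimetres (Table 19).

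SAP 4.4.1 tabulates solicited events by group, after each dose and overall, with exact confidence intervals. A site event recorded after co-administered vaccines is counted once. No safety table is split by vaccine, site or arm. Elimination code 1070 (SAP 3.1.3, Table 2) treats side as an issue only when both Co-Ad vaccines go into the same arm. It applies only to the per-protocol sets, whereas safety uses the Exposed Set.

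**The concern.** Protocol 4.2 sets out to compare co-administration with separate administration. At the RSV site the groups differ in two ways at once: whether the COVID-19 vaccine was given at the same visit, and which arm was used. Randomisation does not balance a factor that the protocol assigns by group.

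A scale based on limb movement and daily activity could plausibly grade the same soreness differently in the arm a person uses more. A reader who sees more arm pain in Co-Ad could then attribute it to co-administration when part of it may come from the arm. Neither document mentions the difference or provides a table that avoids it.

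**Working it through.** **Assigned arm, from Table 5**

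| Vaccine | Co-Ad | Control |
|---|---|---|
| COVID-19 | Non-dominant, Day 1 | Non-dominant, Day 1 |
| RSV | Dominant, Day 1 | Non-dominant, Day 31 |

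The COVID-19 row is balanced in arm and day. In the RSV row, arm coincides with group except for footnote exceptions, which are not random.

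**Inputs.** About 415 participants per group (Protocol 4.1). The documents give no site-event rate and no dominance effect. The following are assumptions: rate p = 15% at a non-dominant RSV site, q = 15% at the COVID-19 site, independent sites, no true co-administration effect, and dominant to non-dominant risk ratio RR = 1.0 to 1.3.

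**RSV site alone (a contrast the SAP does not plan).** Shift = p(RR − 1). SE = √{[p(1 − p) + pRR(1 − pRR)]/415}.
- RR 1.3: 0.15 × 0.3 = 4.5 points; SE = √[(0.1275 + 0.1570)/415] = 2.6 points; about 1.7 SE.

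**Overall any-site rate (the SAP's counting).** Rate = 1 − (1 − RSV-site rate)(1 − q), so the shift shrinks by the factor 1 − q.
- Control: 1 − 0.85 × 0.85 = 27.8%.
- Co-Ad, RR 1.0: also 27.8%; shift 0.
- Co-Ad, RR 1.1: 1 − 0.835 × 0.85 = 29.0%; shift 1.3 points; SE 3.1.
- Co-Ad, RR 1.3: 1 − 0.805 × 0.85 = 31.6%; shift 3.8 points; SE = √[(0.2775 × 0.7225 + 0.3158 × 0.6843)/415] = 3.2; about 1.2 SE.

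With COVID-19 site rates of 30% to 50%, the factor 1 − q is 0.7 to 0.5, so an RSV-site shift of 5 points becomes 3.5 to 2.5 points overall.

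**Per-dose tables: Co-Ad dose against Control RSV dose.** Two sites are set against one. With no dominance effect, the difference is (1 − p)q.
- At 15% and 15%: 0.85 × 0.15 = 12.8 points.
- RSV-site rates 30% to 60%, COVID-19 site rates 30% to 50%: from 0.4 × 0.3 = 12 to 0.7 × 0.5 = 35 points.
- At 15% and 15% with RR 1.3: 31.6 − 15.0 = 16.6 points, of which 3.8 come from dominance.

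The number of sites therefore outweighs dominance in these tables.

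**COVID-19 site after the Day 1 dose.** Assigned arm, day and number of sites are the same in both groups, so the shift from dominance is zero whatever RR is. At an assumed 15% rate the SE of the difference is √(2 × 0.1275/415) = 2.5 points, a 95% half-width of about 4.9 points.

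**The case against.** The strongest reply is that the safety estimand (Protocol 3.2.2) compares whole regimens under a treatment policy. Co-Ad requires separate arms, so one of its injections has to go in the dominant arm, and arm use is part of what was randomised. That stands: the regimen comparison is a valid randomised one. What is not identified is the part due to co-administration at the RSV site, and no listed analysis isolates it.

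It also stands that the mechanism is narrow. Redness and swelling are measured in millimetres, and Grade 3 pain includes pain at rest. The SAP's tables of individual events cover any grade, Grade 3 and medically attended events; a category of at least Grade 2 appears only in the derivation rules (SAP 6.3.5.3).

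Three stronger readings are tempting, and the documents do not support them:
- A reader might take the 4.5-point, 1.7-SE figure as the bias in the planned results. It belongs to an RSV-site contrast that the SAP does not plan, and it rests on an assumed effect.
- A reader might conclude that the RSV sides never overlap. The footnote lets some Control participants receive the vaccine in the dominant arm, though such exceptions would probably be few and would not be random.
- A reader might infer that Table 5 must give each vaccine the same side in both groups. Because Co-Ad uses both arms, that would force one Control injection into the dominant arm, against the footnote's preference. It is an administration rule for the sponsor to settle.

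**Conclusion.** The point holds with limited weight. By assignment, RSV-site local reactions are largely aliased with arm dominance, and the plan neither says so nor offers a comparison free of it. The effect is plausible mainly for activity-graded pain.

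Under the assumptions above, the overall any-site rate shifts by 0 to about 3.8 points, with an SE of about 3.2. The true size is unknown, a ratio below 1 would reverse the sign, and correlation between a person's two sites would change the figures. The imbalance of two sites against one in the per-dose tables is larger and needs the same caution.

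No safety hypothesis is tested. The primary GMT ratios, the sample size and the type I error do not depend on the side of injection.

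**What to change.** In SAP 4.4.1:

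1. Add a by-site tabulation of solicited administration site events. At the COVID-19 vaccine site after the Day 1 dose, give the between-group difference with a 95% CI by the Miettinen and Nurminen method, which SAP 4.1.1 already names for differences in proportions.
2. Tabulate, by group and vaccine, the side actually used, as dominant or non-dominant.
3. Footnote the site-event tables: RSV-site and any-site differences between groups also reflect arm dominance and, in the per-dose tables, the number of injection sites.

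Separately, the sponsor should reconcile the Table 5 laterality entries with the table's own footnote, since the Co-Ad entry for the RSV vaccine and the stated preference pull apart. This review takes no position on which arm is right.

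The cost is a few extra tables. Items 1 and 2 need events recorded by site and the arm recorded relative to handedness. The SAP's single-count rule and code 1070 suggest that site and arm are captured, but the documents do not show the diary card or the eCRF page, so this should be confirmed. The clean comparison covers only the COVID-19 site and says nothing about the RSV site. It also remains open-label, so differences in reporting are not removed.
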